13.4.4 Interim Analyses and Stopping Rules

A 3+3 dose-escalation algorithm will be followed to insure safety. After the completion of the dose-determining part and prior to enrolling on the expansion cohort (phase II), safety and preliminary efficacy interim analysis will be performed.

13.5 Sample Size and Power

Determination of phase I sample size

3+3 dose escalation scheme will be utilized, with 3 to 6 evaluated at each dose level. It is expected that maximum of 12 patients will be enrolled.

Determination of phase II sample size

Entospletinib has been associated with an ORR 61% at the end of study and obinutuzumab in combination with chlorambucil has led to an ORR of 77.3% and CR rate of 20.7% after completion of therapy [22]. The null hypothesis that the true CR rate is 20% will be tested against a one-sided alternative. A sample size of 17 achieves 83% power to detect a difference in complete response of 0.30 (0.2 vs. 0.5) using a one-sided binomial test with the target significance level of 0.05. The actual significance level achieved by this test is 0.0984. If more than equal to 7 patients achieve complete response, then conclude the regimen is effective, and consider a larger/next phase of clinical trial (phase III).

A sample size of 17 subjects treated at the RP2D provides a reasonable probability to detect a rare adverse event, for example, 83% chance of detecting an adverse event with an incidence of 10% (Table 14). Subjects with CLL treated at the RP2D in Phase I will be counted towards Phase II enrollment. Anticipating an attrition rate of 15%, a total of 20 patients per protocol population will need to be enrolled.

Table 14. Probability of detecting an AE with a specified incidence rate at the RP2D

AE incidence	N=17: Probability of detect an AE
0.01	0.16
0.05	0.58
0.10	0.83
0.15	0.94
0.20	0.98

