13.4.1 Analysis of Primary Endpoints

The MTD will be determined according to 3+3 dose escalation design using the dose determining set. Adverse events will be graded and categorized according to the CTCAE v4.03. All adverse events will be tabulated and summarized by major organ category, grade, anticipation, and drug attribution. SAE specific incidence and exact 95% confidence interval will be provided where appropriate.

The CR will be computed and presented together with the exact 95% confidence interval (CI), using the method of Clopper and Pearson. A null hypothesis of a 20% CR will be rejected if at least 7 of 17 patients achieve a CR and a treatment arm will not be considered further if this threshold is not reached.

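### The stated actual significance level of 0.0984 is wrong: at least 7 CRs in 17 against a 20% null has an exact one-sided type I error of 0.0377

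*Combined protocol and SAP*

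**What the plan says.** Section 13.5 (Sample Size and Power) sets up the phase II test: "The null hypothesis that the true CR rate is 20% will be tested against a one-sided alternative". It takes 17 patients, a true CR rate of 50% as the alternative, and 83% power, "using a one-sided binomial test with the target significance level of 0.05". The next sentence reads "The actual significance level achieved by this test is 0.0984". The decision rule follows: "If more than equal to 7 patients achieve complete response, then conclude the regimen is effective".

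Section 13.4.1 (Analysis of Primary Endpoints) gives the same rule: "A null hypothesis of a 20% CR will be rejected if at least 7 of 17 patients achieve a CR". It adds that below this threshold the treatment is not taken further. The same section says the CR rate will be "presented together with the exact 95% confidence interval (CI), using the method of Clopper and Pearson".

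**The concern.** An exact test built to a 0.05 target should have an achieved level at or below 0.05. Here the achieved level is given as nearly twice the target, with no explanation, in the same paragraph as a power figure that looks right for the stated cutoff. Either the cutoff, the sample size or the significance level had to be wrong.

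This matters because the count of CRs is the whole phase II decision: a single-stage, single-arm design in which 7 CRs leads to a declaration of efficacy and consideration of phase III, and fewer ends development of the arm. As written, the plan tells readers that a regimen with a true CR rate of 20% has about a 10% chance of being declared effective. A reader could discount a genuine positive result on that basis. Someone could also raise the cutoff to 8 to repair a problem that does not exist, and power would fall from 83% to 69%.

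**Working it through.** **Inputs.** From Section 13.5: null rate p0 = 0.20, alternative p1 = 0.50, n = 17, one-sided, target 0.05, stated power 83%, stated actual level 0.0984. From Sections 13.5 and 13.4.1: reject if the number of CRs, X, is at least 7.

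**Formula.** For X ~ Binomial(n, p), P(X ≥ c) = 1 − Σ C(n, k) p^k (1 − p)^(n−k), summed over k = 0 to c − 1.

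**Step 1: the plan's power.** With n = 17, c = 7, p = 0.50, P(X ≤ 6) = 0.1662, so P(X ≥ 7) = 0.834. The stated 83% reproduces, which confirms that the power was computed for this cutoff and sample size.

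**Step 2: the significance level of the same rule.** With p = 0.20 the terms for k = 0 to 6 are 0.0225, 0.0957, 0.1914, 0.2393, 0.2094, 0.1361 and 0.0680. They sum to 0.9623 (before rounding of the terms), so P(X ≥ 7) = 1 − 0.9623 = **0.0377**. The stated 0.0984 does not reproduce. The ratio to the true value is 0.0984 / 0.0377 = 2.6, and to the target 0.0984 / 0.05 = 1.97.

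**Step 3: could 0.0984 belong to another rule?** Neighbouring cutoffs at n = 17:

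| Success if CRs at least | Level at 20% | Power at 50% |
|---|---|---|
| 5 | 0.2418 | 0.975 |
| 6 | 0.1057 | 0.928 |
| 7 | 0.0377 | 0.834 |
| 8 | 0.0109 | 0.685 |

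None gives 0.0984. Other readings of the rule of 7 in 17 fail as well:

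- Two-sided exact test: 0.0602. Doubled one-sided tail: 0.0753.
- Normal approximation: 0.0145, or 0.0301 with continuity correction. For a cutoff of 6 these are 0.0575 and 0.1015.
- Null rate of 20.7%, the CR rate that Section 13.5 cites for obinutuzumab with chlorambucil: 0.0446.
- Cutoff of 7 applied to all 20 patients to be enrolled: 0.0867.
- A search over n = 5 to 59, every cutoff, and null rates of 0.10, 0.15, 0.20, 0.207, 0.25, 0.30 and 0.50: no match.

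For 7 of 17 to have a level of 0.0984 the null rate would have to be about 0.245, a value that appears nowhere in the plan.

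**Step 4: the interval at the success boundary.** Clopper-Pearson limits for 7/17 (41.2%):

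- Two-sided 95%: 18.4% to 67.1%, which contains 20%.
- Two-sided 90%, whose lower limit matches a one-sided 5% test: 21.2% to 63.6%, which excludes 20%.

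At 8/17 the 95% lower limit is already 23.0%, so the mismatch arises at one result only, the boundary itself.

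**The case against.** The arithmetic is not in dispute; the objections concern its weight and the remedy.

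- **It is a reporting error.** The rule is the same in both sections and meets the 0.05 target at n = 17. The misprint makes the design look worse than it is and cannot by itself create a false positive; any reader can recompute it from the same paragraph. This is right about direction. It does not remove the need to correct a wrong type I error for the primary endpoint.

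- **The interval is not an error.** Section 13.4.1 rests rejection on the count, and a two-sided 95% interval presented as description beside a one-sided 0.05 test is common. Its lower limit corresponds to a one-sided 0.025 level, so the two can differ without contradicting each other. This stands: the interval is a matter of clear presentation at one possible result.

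- **0.0377 holds only for exactly 17 analysed patients.** Section 13.5 says: "Anticipating an attrition rate of 15%, a total of 20 patients per protocol population will need to be enrolled". Sections 11.0 and 13.3 make everyone with at least one dose evaluable for efficacy. With the cutoff held at 7, the exact level is 0.0513 at n = 18, 0.0676 at n = 19 and 0.0867 at n = 20. This stands as a condition on the corrected figure. It does not rescue 0.0984, which none of these sizes yields.

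**Conclusion.** The concern holds. For the rule as written, the exact one-sided type I error is 0.0377, not 0.0984. The sample size, cutoff, 83% power and 0.05 target agree with one another; the stated actual level is the only figure that does not fit. The test is not too loose; its headline error rate is misreported, by a factor of 2.6. No other part of the documents corrects or explains it.

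The conclusion rests on an exact binomial test with p0 = 0.20, a cutoff of 7 and exactly 17 patients in the analysis. The interval point is secondary, and the core correction does not depend on it.

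**What to change.** In Section 13.5, replace 0.0984 with 0.0377 and say that this is the exact one-sided level of at least 7 CRs in 17 analysed patients at a null rate of 20%. Leave the cutoff, the sample size of 17 and the power statement unchanged.

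Optionally, add one sentence to Section 13.4.1: a two-sided 90% Clopper-Pearson interval (equivalently, a one-sided 95% lower bound) accompanies the decision, and the 95% interval is descriptive.

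The cost is one corrected figure with its condition and, if adopted, one sentence. No patients, procedures or timelines change.

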13.6 Randomization Method

Not applicable

13.7 Handling of Missing Data

For missing data, we will evaluate whether or not the other time points can be used to fulfill the primary and secondary data. No missing data will be imputed. Whenever possible, all available data will be included in the analysis. A sample size for each analysis will be clearly stated along with the reason for exclusion, if any subject is excluded from the analysis due to missing data.

Data Monitoring Committee

The Knight Data Safety Monitoring Committee (DSMC) at the OHSU Knight Cancer Institute will be to monitor safety data.

REFERENCES

1. SEER Cancer Statistics Review, 1975-2010 [Internet]. 2013.

6. Shaw R.K. BDR, Silberman H.R., and Frei E. III. A Study of prednisone in Chronic Lymphocytic Leukemia. *Blood*. 1961;17(2):182-95.

APPENDIX A Obinutuzumab Prescribing Information

The most current obinutuzumab prescribing information can be found at the link below.

http://www.gene.com/download/pdf/gazyva_prescribing.pdf

APPENDIX B Creatinine Clearance Formula

CrCL should be calculated using the Cockcroft-Gault formula:

$$\text{CrCL} = [(140 - \text{age}) \times \text{Weight (kg)} \times 0.85 \text{ (if female)}] / [72 \times \text{serum creatinine (in mg/dL)}].$$

APPENDIX C Strong and Moderate Inhibitors and Inducers of CYP Enzymes

CYP Inhibitors

	Strong	Moderate
CYP2C9	
 - fluvoxamine - ticlopidine 	
 - fluconazole - esomeprazole - fluoxetine - moclobemide - omeprazole - voriconazole
CYP3A	
 • boceprevir • clarithromycin • conivaptan • grapefruit juice • indinavir • itraconazole • ketoconazole • lopinavir/ritonavir • mibepradil • nefazodone • nelfinavir • posaconazole • ritonavir • saquinavir • telaprevir • telithromycin • voriconazole 	
 - amprenavir - aprepitant - atazanavir - ciprofloxacin - darunavir/ritonavir - diltiazem - erythromycin - fluconazole - fosamprenavir - grapefruit juice - imatinib - verapamil

CYP Inducers

	Strong	Moderate
CYP2C9		
 • carbamazepine • rifampin
CYP3A	
 - avasimibe - carbamazepine - phenobarbital 	
 • bosentan • efavirenz • etravirine

	
- phenytoin- rifampin- St. John's wort	
• modafinil• nafcillin
--	--	---

APPENDIX D ECOG Performance Status*

Grade	ECOG
0	Fully active, able to carry on all pre-disease performance without restriction
1	Restricted in physically strenuous activity but ambulatory and able to carry out work of a light or sedentary nature, e.g., light house work, office work
2	Ambulatory and capable of all selfcare but unable to carry out any work activities. Up and about more than 50% of waking hours
3	Capable of only limited selfcare, confined to bed or chair more than 50% of waking hours
4	Completely disabled. Cannot carry on any selfcare. Totally confined to bed or chair
5	Dead

* As published in Am. J. Clin. Oncol.:

APPENDIX E LPL Assessment

Category	Finding
Laboratory	Serum monoclonal IgM > 0.5 g/dL Hemoglobin level < 10 g/dL Platelet count < 100 x 10 ⁹ /L
Laboratory + symptoms	Cryoglobulinemia with symptoms Hyperviscosity with symptoms
Physical Findings	Bulky adenopathy Organomegaly
Symptoms	Recurrent fevers Night sweats Weight loss Fatigue Symptomatic neuropathies
Organ Disease	Nephropathy Amyloidosis
Pathology	Disease Transformation

[figure not shown]
Definitions of Response for Waldenstrom's Macroglobulinemia

- Complete response (CR): Absence of serum monoclonal IgM protein by immunofixation; normal serum IgM level and complete resolution of extramedullary disease, i.e. lymphadenopathy and splenomegaly if present at baseline; morphologically normal bone marrow/aspirate and trephine biopsy.
- Very good partial response: Monoclonal IgM protein is detectable; $\geq 90\%$ reduction in serum IgM level from baseline; complete resolution of extramedullary disease, i.e. lymphadenopathy and splenomegaly if present at baseline; no new signs or symptoms of active disease.
- Partial response (PR): Monoclonal IgM protein is detectable; $\geq 50\%$ but < 90% reduction in serum IgM level from baseline; reduction of extramedullary disease, ie, lymphadenopathy and splenomegaly if present at baseline; no new signs or symptoms of active disease.
- Minor response: Monoclonal IgM protein is detectable; $\geq 25\%$ but < 50% reduction in serum IgM level from baseline; no progression in extramedullary disease, i.e. lymphadenopathy/splenomegaly if present at baseline; no new signs or symptoms of active disease.
- Stable disease: Monoclonal IgM protein is detectable; < 25% reduction and < 25% increase in serum IgM level from baseline; no new signs or symptoms of active disease.
- Progressive disease: $\geq 25\%$ increase in serum IgM level from lowest nadir (requires confirmation) and/or progression in clinical features attributable to the disease.

APPENDIX F Pre-clinical data

[figure not shown]
SYK Inhibition abrogates BAFF-mediated CLL survival

Fig. 1

[figure not shown]
CLL cells were co-cultured with control, BAFF- or CD40L-expressing stroma for 24 h. p65/p52 activity was determined using NF κ B TransAm Assay. *-p<0.05, ** - p<0.01 compared to 0 h (prior to co-culture, set at 1, dotted line).

Fig. 2

[figure not shown]
CLL cells were co-cultured with BAFF-expressing stroma for 24 h, incubated with the indicated drugs for 24 h, and assayed for apoptosis using flow cytometry (Annexin V-positive cells shown).

Fig. 3

CLL cells were co-cultured with BAFF-expressing stroma for 24 h and incubated with the indicated drugs for 224 hours. p65/p52 activity was determined using NF κ B TransAm Assay. *-p<0.05 compared to untreated control.

Fig. 4

CLL cells were co-cultured with BAFF-expressing stroma for 24 h, incubated with the indicated drugs for 24 h and subjected to immunoblotting.

APPENDIX G Response Criteria for FL, MZL and MCL

Response criteria for subjects with Follicular Lymphoma, Marginal Zone Lymphoma and Mantle Cell Lymphoma

Complete Response (CR)

1. Complete disappearance of all detectable clinical evidence of disease and disease-related symptoms if present prior to therapy. Typically FDG-avid lymphoma: in patients with no pre-treatment PET scan or when the PET scan was positive before therapy, a post-treatment residual mass of any size is permitted as long as it is PET negative. Variably FDG-avid lymphomas/FDG avidity unknown: in patients without a pretreatment PET scan, or if a pretreatment PET scan was negative, the designation of CR requires all nodal indicator lesions to regress to the size of normal lymph nodes. Lymph nodes that were > 15 mm in GTD regardless of the short axis diameter at the screening tumor assessment must regress to ≤ 15 mm in GTD regardless of the short axis diameter. Lymph nodes that were 11 to 15 mm in GTD and > 10 mm in the short axis diameter at the screening tumor assessment must regress to ≤ 10 mm in the short axis diameter.

2. The spleen and/or liver, if considered enlarged prior to therapy on the basis of a physical examination or CT scan, should not be palpable on physical examination and should be considered normal size by imaging studies, and nodules related to lymphoma should disappear. However, determination of splenic involvement is not always reliable because a spleen considered normal in size may still contain lymphoma, whereas an enlarged spleen may reflect variations in anatomy, blood volume, the use of hematopoietic growth factors, or causes other than lymphoma.

3. If the bone marrow was involved by lymphoma prior to treatment, the infiltrate must have cleared on repeat bone marrow biopsy. The biopsy sample on which this determination is made must be adequate (> 20 mm unilateral core). If the sample is indeterminate by morphology, it should be negative by immunohistochemistry. A sample that is negative by immunohistochemistry but demonstrating a small population of clonal lymphocytes by flow cytometry will be considered a CR until data become available demonstrating a clear difference in patient outcome.

Partial Remission (PR)

1. $\geq 50\%$ decrease in sum of the product of the diameters (SPD) of up to 6 of the largest dominant nodes or nodal masses. These nodes or masses should be selected according to the following: (a) they should be clearly measurable in at least 2 perpendicular dimensions; (b) if possible they should be from disparate regions of the body; (c) they should include mediastinal and retroperitoneal areas of disease whenever these sites are involved.

2. No increase in the size of the other nodes, liver, or spleen.

3. Splenic and hepatic nodules must regress by $\geq 50\%$ in their SPD or, for single nodules, in the greatest transverse diameter.

4. With the exception of splenic and hepatic nodules, involvement of other organs is usually assessable and no measurable disease should be present.

5. Bone marrow assessment is irrelevant for determination of a PR if the sample was positive prior to treatment. However, if positive, the cell type should be specified (e.g., large-cell lymphoma or small neoplastic B cells). Patients who achieve a complete remission by the above criteria, but who have persistent morphologic bone marrow involvement will be considered partial responders.

6. No new sites of disease should be observed (e.g., nodes > 1.5 cm in any axis).
7. Typically FDG-avid lymphoma: for patients with no pretreatment PET scan or if the PET scan was positive before therapy, the post-treatment PET should be positive in at least one previously involved site.
8. Variably FDG-avid lymphomas/FDG-avidity unknown: for patients without a pretreatment PET scan, or if a pretreatment PET scan was negative, CT criteria should be used.
9. In patients with follicular lymphoma, a PET scan is only indicated with one or at most two residual masses that have regressed by more than 50% on CT; those with more than two residual lesions are unlikely to be PET negative and should be considered partial responders.

Stable Disease (SD)

1. Failing to attain the criteria needed for a CR or PR, but not fulfilling those for progressive disease (see below).
2. Typically FDG-avid lymphomas: the PET should be positive at prior sites of disease with no new areas of involvement on the post-treatment CT or PET.
3. Variably FDG-avid lymphomas/FDG-avidity unknown: for patients without a pretreatment PET scan or if the pretreatment PET was negative, there must be no change in the size of the previous lesions on the post-treatment CT scan.

Relapsed Disease (RD; after CR) or Progressive Disease (PD; for Patients with PR or SD)

Progressive/Relapsed Disease

1. Lymph nodes should be considered abnormal if the long axis is > 1.5 cm, regardless of the short axis. If a lymph node has a long axis of 1.1–1.5 cm, it should only be considered abnormal if its short axis is > 1.0 . Lymph nodes ≤ 1.0 cm by ≤ 1.0 cm will not be considered as abnormal for relapse or progressive disease.
2. Appearance of any new lesion more than 1.5 cm in any axis during or at the end of therapy, even if other lesions are decreasing in size. Increased FDG uptake in a previously unaffected site should only be considered relapsed or progressive disease after confirmation with other modalities.
3. At least a 50% increase from nadir in the SPD of any previously involved nodes, or in a single involved node, or the size of other lesions (e.g., splenic or hepatic nodules). To be considered progressive disease, a lymph node with a diameter of the short axis of less than 1.0 cm must increase by $\geq 50\%$ and to a size of 1.5×1.5 cm or more than 1.5 cm in the long axis.
4. At least a 50% increase in the longest diameter of any single previously identified node more than 1 cm in its short axis.
5. Lesions should be PET positive if observed in a typical FDG-avid lymphoma or the lesion was PET positive before therapy unless the lesion is too small to be detected with current PET systems (< 15 mm in its long axis by CT).

6. Measurable extranodal disease should be assessed in a manner similar to that for nodal disease. For these recommendations, the spleen is considered nodal disease.

Notes: Bone marrow status is evaluated as follows:

- Positive: Unequivocal cytological or architectural evidence of malignancy.
- Negative: No aggregates or only a few well-circumscribed lymphoid aggregates.

APPENDIX H Safety Reporting Fax Cover Sheet

A Member of the Roche Group

GENENTECH SUPPORTED RESEARCH

AE/SAE [contact]

Alternate [contact]

Page 1 of ____

Genentech Study Number	
Principal Investigator	
Site Name	
Reporter name	
Reporter Telephone #	
Reporter Fax #	
Initial Report Date	/ / dd / mmm / yyyy
Follow-up Report Date	/ / dd / mmm / yyyy
Patient Initials (Please enter a dash if the patient has no middle name)	____ - ____ - ____

SAE or Safety Reporting questions, contact Genentech Safety: [contact]

PLEASE PLACE MEDWATCH REPORT or SAFETY REPORT BEHIND THIS COVER SHEET

Appendix I Response criteria for Hairy cell leukemia (determined by the Consensus Resolution response criteria [47])

Complete response (CR)

- A morphological absence of hairy cells in the blood and bone marrow
- A normalization of any organomegaly and cytopenias

Partial response (PR)

- A normalization of cytopenias
- $\geq 50\%$ reduction in organomegaly and bone marrow hairy cells.

All other responses are considered as no response (NR)

Relapse after CR

- Reappearance of hairy cells in the blood or bone marrow
- Development of cytopenias and/or splenomegaly on physical examination

Relapse after PR

- $>50\%$ increase of residual disease

LIST OF ABBREVIATIONS

The following abbreviations and special terms are used in this study protocol.

Term	Explanation
AE	Adverse Event
ALC	Absolute lymphocyte count
ALT	Alanine aminotransaminase
ANC	Absolute neutrophil count
aPTT	Activated partial thromboplastin time
AST	Aspartate aminotransferase
BCR	B-cell receptor
BID	Twice daily
BTK	Bruton tyrosine kinase
CBC	Complete blood count
CCRC	Clinical Cancer Review Committee
CIRS	Cumulative Illness Rating Scale
CLL	Chronic lymphocytic leukemia
CPHS	Committee for the Protection of Human Subjects
CR	Complete response
CrCL	(estimated) Creatinine clearance
CRi	Complete response with incomplete marrow recovery
CRMS	Knight Clinical Research Management System
CT	Computed tomography
CTO	Clinical Trials Office
DLT	Dose-limiting toxicity
DSMC	Data and Safety Monitoring Committee
eCRF	Electronic case report form
EFS	Event-free survival
FISH	FISH
FL	Follicular lymphoma
IGHV	Immunoglobulin heavy chain gene
IHC	Immunohistochemistry
IRB	Institutional Review Board
IRR	Infusion-related reaction
IV	Intravenously
IWCLL	International Workshop on Chronic Lymphocytic Leukemia
KCI	Knight Cancer Institute
LPL	Lymphoplasmacytic lymphoma
LVEF	Left Ventricular Ejection Fraction
LDH	Lactate dehydrogenase
MCL	Mantle cell lymphoma
MTD	Maximum tolerated dose
MZL	Marginal zone lymphoma
nPR	Nodular partial response
OHSU	Oregon Health and Science University
ORR	Objective response rate
OS	Overall survival

PD	Pharmacodynamic
PFS	Progression-free survival
PI	Principal investigator
PI-3K	Phosphoinositide-3 kinase
PK	Pharmacokinetic
PO	By mouth
PR	Partial remission
RP2D	Recommended Phase II dose
SAE	SAE
SLL	Small lymphocytic lymphoma
t½ - half-life	Half-life
ULN	Upper limit of normal
USPI	United States prescribing information
WBC	White blood cells
ZAP-70	Zeta chain-associated T-cell receptor protein kinase 70 kDa
